- iv. Fasting Blood Draw: Glucose, insulin, total cholesterol, HDL-C, LDL-C, triglycerides, creatinine, CK, and ALT will be measured in fasting blood samples.
- v. Insulin Sensitivity: Glucose and insulin, and insulin sensitivity will be calculated using a minimal model program following the IVGTT.
- vi. Cardiovascular Function: Heart rate and stroke volume (and finometer) will be measured under resting conditions.
- **B. Study Type and Design:** This study is a longitudinal, repeated measures, double-blinded design with participants randomly assigned to placebo, low (20 mg/d) or high (80 mg/d) atorvastatin therapy for a one year dose-response study. We expect to screen approximately of 500 participants to enroll (randomize) a maximum of 60 participants. The goal is to have 45 participants complete all study procedures (15 in each group). Repeated measures design allows each subject to serve as their own control. Placebo groups are included to account for potential changes in muscle mitochondrial function independent of statin therapy over the 1 year dose-response.

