is removed from the incision. Sterile gauze is placed on the incision site and pressure is applied with an ice pack for ~5 minutes. The site is then closed with a steri-strip and band-aid. Sterile gauze is then applied on top of the band-aid and pressure is applied by wrapping coban around the thigh. Approximately 100-200 mg of skeletal muscle will be collected during each biopsy in one pass. In the case where less muscle is harvested per pass, one more additional pass will be taken with the participants consent. The tissue collected is dissected free of connective tissue and separated for mitochondrial function studies or frozen in liquid nitrogen for subsequent biochemical analyses as done previously (13, 61). [name] and his team have performed over 300 skeletal muscle biopsies without incidence since starting his independent lab in 2005. Additionally, Neurologists who study various muscle diseases regularly perform the technique at KUMC. After analysis for current project is complete any remaining muscle samples will be stored indefinitely for future research. Muscle biopsies will be repeated at 1, 6, and 12 months. See appendix for letter from IRB Director ([name]) at [name] previous institution (MU) stating his record for conducting muscle biopsies and a letter of support for the procedure from [name], the Director of the CTSU. Biopsies will be taken by [name] or by [name] who has been trained during his PhD work at Oregon State and by [name] here at KUMC

- vi. Near Infrared Spectroscopy (NIRS): Muscle mitochondrial functional capacity will be measured non-invasively using a NIRS technique developed by [name], a member of the research team at ECU (46). Participants will perform submaximal knee extension exercise to increase muscle oxygen consumption (mVO₂) and the recovery kinetics is determined during a series of repeated arterial occlusions. The mVO₂ data are fit to a mono-exponential function to calculate the rate constant, which is directly related to the mitochondrial respiratory capacity. NIRS will be repeated at 1, 6 and 12 months.

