- xi. Exercise Testing: Whole body steady state submaximal O₂ consumption will be determined during a standard 6 min treadmill test (2.5mph) to determine VO₂ cost. Participants will then complete a ramped treadmill test (Bruce protocol) to determine cardiorespiratory fitness (VO₂ peak) and peak heart rate as previously described (13). We will also investigate post exercise oxygen consumption and heart rate at 60, 90, 120, and 300 seconds after cessation of the max test to determine if exercise recovery is impacted by statins. Blood will be sampled for measurement of CK 20-30 minutes following the maximal exercise to assess potential muscle damage. Exercise testing will be repeated at 1, 6, and 12 months.
- xii. Cardiovascular Function: These measures include both heart rate and stroke volume performed under both resting and sub-maximal exercise conditions (performed on separate days) (80). Stroke volume will be estimated by finometer placed on finger (80). Cardiovascular function will be repeated at 6 and 12 months.
- xiii. Physical Activity Monitoring: Physical activity levels and sedentary time will be assessed by pedometers and accelerometers for 5 day periods. Physical activity monitoring will be repeated at 1, 6 and 12 months.
- xiv. Statin Therapy Intervention: Once participants have successful completed baseline testing, the participant will be randomly assigned to 1 of 3 groups (1:1:1 ratio). Statins will be prescribed as a placebo or at a dosage of 20 or 80 mg/day (atorvastatin; Lipitor) by the study physician at KUMC, [name], MD. Participants and research team will be blinded to the type and dose of statin. Statins will be dispensed by KUMC investigational pharmacy at regular intervals during the participant's enrollment in the study. The study physician will provide care for any problems associated with the statin treatment after unblinding by Data Safety Monitoring Board, [name]. All doses fall within the norms of recent recommendations and are given chronically (2).

F. Risk/benefit assessment:

a. Potential risks:

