 In summary, the benefits to the participants are substantial, and the information detailing the impact of statins on mitochondrial, metabolic, and cardiovascular function have the promise of helping millions of patients and physicians evaluate the risk to benefit ratio of statin therapy. There are risks associated with the study, but the experience and medical expertise of the research team should keep these at a minimum, and our track record with exercise and diet research indicates that this diligence has been effective.
- G. Location where study will be performed: All portions of the study will occur at KUMC.
- H. Collaboration: This is a Multi-PI application from Drs. [name] and [name] from the University of Kansas Medical Center and East Carolina University, respectively. Both investigators have been conducting research on statins for several years. The project was born out of a common desire to combine their individual expertise to investigate the mechanisms underlying skeletal muscle complications associated with statin therapy in a repeated measures, longitudinal design. Due to the scope of the design (i.e., number of participants, duration) and complexities of the primary outcome measures, it was felt a multi-PI, multi-institutional approach represented the most efficient and statistically valid means of completing the project and thereby making truly sustained impact of the field. Each investigator has trained at/frequently visited the other institute and is quite familiar with the research environments. Standard operating procedures will be developed for all common testing and primary outcome measurements, and each investigator and their key personnel will visit the other institute prior to commencing the study to conduct trial runs to insure continuity. The PIs will share responsibility for fiscal and research management. Using the multi-PI approach with two investigators with translational research experience and

complimentary analytical expertise dramatically increases the power of the study and the likelihood of successfully completing the proposed aims.

I. Single IRB Review for a Multi-site study: NA

J. Personnel who will conduct the study, including:

- 1. Indicate, by title, who will be present during study procedure(s): PI, Study Coordinator
- 2. Primary responsibility for the following activities, for example:
 - a. Determining eligibility: PI, Study Coordinator
 - b. Obtaining informed consent: PI, Study Coordinator

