 - c. Providing on-going information to the study sponsor and the IRB: PI, Study Coordinator
 - d. Maintaining participant's research records: PI, Study Coordinator
 - e. Completing physical examination: PI, CTSU Nurse
 - f. Taking vital signs, height, weight: CTSU Nurses
 - g. Drawing / collecting laboratory specimens: CTSU Nurses
 - Performing / conducting tests, procedures, interventions, questionnaires: PI,
 Study Coordinator
 - i. Completing study data forms: Study Coordinator
 - j. Managing study database: PI

K. Assessment of Subject Safety and Development of a Data and Safety Monitoring Plan

- **a. Key personnel:** [name], [name], [name], [name], study physician at KUMC and [name], study physician at ECU.
- b. Plan for safety monitoring and review: [name] will serve as the Chair of the Data Safety Monitoring Board and will convene every 6 months with the other members, Drs. [name] and [name] to make decisions on safety of the participants. Enrollment data will also be reviewed twice a year by the DSMB. In addition, data will be reviewed on a yearly basis with the biostatistician, [name] to determine if the studies should be shortened do to either no measured effect or due to effects that are greater than what power calculations indicated. If problems occur with participants, blinded study staff will alert [name]. [name] will have access to dose and type of statin and will consult the study physicians/cardiologist to make a decision on whether the subject should be removed from the study for safety concerns. The PI and other key personnel will be examining research data on a subject to subject basis to ensure it is accurate and to address any potential problems that may arise with the protocols. In addition, Drs. [name] and [name] will discuss data at least once per month through in person meetings or by phone to ensure that data collection is occurring in a consistent manner at both locations.
- **c. Plan for adverse event reporting:** Adverse events will be defined as any untoward medical occurrence in study participants or others immediately involved in the

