injury. In spite of all safety measures, you might develop medical problems from participating in this study. You must report any suspected illness or injury to the study coordinator immediately. If such problems occur, you will be provided with emergency medical treatment and the investigator will assist you in getting proper follow-up medical treatment. Neither the investigator nor the sponsor will provide compensation for research-related injuries. Payment of lost wages, disability or discomfort is not available. You do not give up any of your rights by signing this form."

IV. Data Collection and Protection

- A. Data Management and Security: All identifiable files, data, and tissue will be coded and stored in secure locations. These data include: study progression, subject numbers, percent completion, data quality, subject retention, adverse events, etc. The PIs at both KUMC and ECU will be responsible for the quality of the data and will supervise the data acquisition with the help of study coordinators. All data will be coded for confidentiality, and only the PI, study coordinator, and study statistician will have access to the code. The results of each test on each subject will be screened by the study coordinator prior to entering on the spreadsheet. This is standard practice in our laboratories. Hard copies are kept in dedicated locked cabinets. Specific coded subject files will be sent to the study statistician for statistical analyses. These analyses will be sent to the PI and study coordinator for dissemination to appropriate co-Is. At the end of participation in the study, each subject will receive a personal data summary of their test results. The study coordinator or a study investigator will discuss the results with the subject. After 1 year, the PI's including the biostatistician, [name] will be un-blinded but the study staff will remain blinded, so that the important research findings can begin to be delineated. This will also allow for [name] to being to examine if the trial is finding more or less significant effects for outcome measures.
- **B. Sample / Specimen Collection:** All participants will be assigned a data code. Blood and tissue samples will be labeled with the participant's data code and stored in a locked freezer. Blood and tissue samples will be stored indefinitely following completion of current project for future research.

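### The PIs are to be unblinded one year after an undefined start, against the stated double blind and while they keep testing and data tasks

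*Combined protocol and SAP*

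**What the plan says.** On blinding:

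- Section II.B (Study Type and Design): "This study is a longitudinal, repeated measures, double-blinded design".
- Section II.E.a.xiv (Statin Therapy Intervention): "Participants and research team will be blinded to the type and dose of statin". No end date and no exception for the PIs is given.
- Section IV.A (Data Management and Security): "After 1 year, the PI's including the biostatistician, [name] will be un-blinded but the study staff will remain blinded". The stated purpose is to let the main findings start to emerge and to see whether effects are larger or smaller than expected.

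On what the PI does:

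- Section II.J (Personnel), on attendance: "who will be present during study procedure(s): PI, Study Coordinator".
- The same section, on testing: "Performing / conducting tests, procedures, interventions, questionnaires: PI", listed jointly with the study coordinator; and on data: "Managing study database: PI".
- Sections II.K.b and IV.E have the PI and other key personnel check research data one participant at a time.
- Section IV.A makes the PIs at both institutions responsible for data quality and for supervising data collection. It also sends the statistician's analyses to the PI and coordinator, without saying that these are pooled over arms.

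On size and schedule, section II.B: "The goal is to have 45 participants complete all study procedures (15 in each group"; section II.E.a.v (Muscle biopsy): "Muscle biopsies will be repeated at 1, 6, and 12 months". Section II.C places the primary comparison at 12 months.

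**The concern.** A blind covering the whole research team and an unblinding of its leaders after one year cannot both be followed unless the year ends after all outcome work is done. The protocol does not say that it does.

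The hypothesis is directional: statins are expected to lower mitochondrial function, fitness and insulin sensitivity. A PI who knows the arm could influence a test that the PI helps to perform, or could question some values more readily than others during participant-level checks. Several secondary outcomes, such as the maximal treadmill test, knee strength and pain ratings, depend on effort or self-report. At stake is whether the month-12 results can be reported as coming from a double-blind trial.

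**Working it through.** **Step 1: the passages side by side.** Sections II.B and II.E.a.xiv blind the research team without limit. Section IV.A lifts the blind for the PIs. Sections II.J, II.K.b, IV.A and IV.E give the PI tasks that touch outcome data. No section moves those tasks to blinded staff after unblinding.

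**Step 2: is the year tied to a date?** No. Some wording points to a trial still running. Section IV.A keeps other staff blinded after the PIs are not, and speaks of what the trial is finding in the present tense. Sections II.K.b and IV.E plan a yearly review of whether to cut the studies short. Section V.B has data analysed during the study so that the team can stop early. This favours a mid-trial reading but does not fix the start.

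**Step 3: inputs for the count.** The plan's completer target reproduces: 3 × 15 = 45. The primary time point is 12 months after the start of treatment. Randomisation follows baseline testing (section II.E.a.xiv), so it comes later than screening or study opening. The plan states no count of assessments after unblinding, so there is no such figure to reproduce.

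**Step 4: formula.** Let tᵢ be the month in which completer i is randomised, with 0 for the first and A for the last. The month-12 assessment falls at tᵢ + 12. With unblinding at month U, count the completers for whom tᵢ + 12 > U. I assume staggered entry, with one completer first and one last, and visits on their nominal dates.

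| Start of the year | U | Condition | Month-12 assessments after unblinding |
|---|---|---|---|
| Study opening or first screening, s months before first randomisation (s > 0) | 12 − s | tᵢ > −s | 45 of 45 |
| First randomisation | 12 | tᵢ > 0 | 44 of 45 (98%) |
| Last randomisation | A + 12 | tᵢ > A | 0 of 45 |
| Each participant's own randomisation | tᵢ + 12 | never met | 0 of 45 |

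None of these four results depends on the accrual period A, as long as A > 0. The last row counts a participant's own visit only; the PIs would still learn the arms of early finishers while later entrants were being tested.

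**Step 5: the denominator.** The figure of 45 is not settled. Section II.B also allows at most 60 randomised. Section II.C plans 27 per group (3 × 27 = 81) and recruits 30 per group (3 × 30 = 90). On any of these totals the count still runs from none to all. That conflict is a separate matter.

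**The case against.** The strongest reply is that harm to the primary outcome is not shown. The primary measure is instrument-based respirometry, done in duplicate on fibre bundles. Section IV.A keeps study staff blinded and has the coordinator screen each result before entry. Section IV.B labels samples with data codes. The personnel list names the PI and coordinator together, so blinded staff could do all testing after the PIs are unblinded. On two of the four clocks, no month-12 visit is affected.

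Most of this stands as a limit on the claim. It does not remove the conflict. The PI has access to the data codes (section IV.A), still manages the database, and still reviews data by participant. That blinded staff would take over the testing is an inference; the protocol does not say so.

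Three stronger readings are tempting and should not be drawn:

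- **That the primary assay is biased.** The documents do not say who runs respirometry, so only a risk can be stated.
- **That a firm share of all biopsies follows unblinding.** Months 1, 6 and 12 give 3 × 45 = 135 post-baseline biopsies, but the months 1 and 6 counts depend on an accrual period that is not given. With even entry and a first-randomisation clock, assumed accrual of 36 months gives 31 + 37 + 44 = 112, and 48 months gives 34 + 39 + 44 = 117. Neither is a bound.
- **That the biostatistician's role contradicts itself**, because section II.C has that person carry out the randomisation and section IV.A unblinds them only later. A list can be generated with coded arms, and the documents do not say who holds the key.

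**Conclusion.** The concern holds as a conflict in the text. Section IV.A cannot be reconciled as written with the double blind of section II.B and the blinded research team of section II.E.a.xiv, and the PIs' outcome-related tasks continue after unblinding. Followed as written, the plan can break the blind before the primary time point.

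Depending on the clock, 0, 44 or 45 of the 45 planned month-12 assessments would follow PI unblinding. This rests on the section II.B completer target and on staggered entry. The mid-trial reading is better supported but not certain. Confidence is high in the conflict; the count shows only how much turns on an undefined phrase. No bias, and no size of bias, is claimed. The point must be fixed, because the wording decides whether none or all of the key assessments fall after unblinding.

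**What to change.** In section IV.A, delete the one-year unblinding of the PIs and state instead:

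> The PIs, coordinators and everyone who tests participants, runs assays, or cleans or manages data remain blinded until database lock, apart from safety unblinding. Before lock, any output by arm goes from the biostatistician to the DSMB only. The PI and coordinator receive pooled output only.

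Change the section IV.A sentence on sending analyses to the PI and coordinator to match. In sections II.K.b and IV.E, state that the yearly review is done by the biostatistician and DSMB, not by the PIs. In section V.B, give the early look to the same two parties.

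A lesser repair would define the start of the year and list the tasks that an unblinded PI gives up. It would remove the ambiguity, but the PIs could still see results by arm before the trial ends.

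The cost is protocol wording in sections II.K.b, IV.A, IV.E and V.B. The PIs lose early sight of results by arm. No visits, participants or staff are added, and the DSMB already exists.

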- C. Sample size, statistical methods, and power calculation: The randomization for study drugs will be carried out by the biostatistician using a computer-based random number generator at a 1:1:1 allocation. Sample size for study is powered on the basis of detecting a difference in mitochondrial respiratory function, the primary outcome measure, between three groups (e.g., placebo, and 20 or 80 mg/d atorvastatin therapy) at 12 months posttreatment. Our pilot study of statin effect on maximal ADP-stimulated O2 consumption rate (JO_2) after 56 days based on 8 participants showed a mean change of 88.5 (pmol/sec/mg) with standard deviation of 59.9 (pmol/sec/mg), which can be standardized into a very large pre-post effect size of -1.48 (Cohen's d). All of these 8 participants experienced a decrease of 11.13% to 66.94% in 56 days, suggesting the decreasing trends are very consistent among participants. The overall decreasing trend of maximal ADP-stimulated O2 consumption rate across all time points also suggests that the decreasing trend will continue beyond 56 days. For the other outcomes variables, insulin-sensitivity and in-vivo O2 recovery kinetics (NIRS), only measurements at baseline and day 56 are available and the observed changes are -0.65 (1.20) (mU/L)⁻¹ min⁻¹ and 19.07 (21.80) mVO₂, which can be standardized into effect sizes of -0.54, and 0.87, respectively. In a much longer study period of 12 month, the within group changes for these variables are expected to be greater. Expecting no change or a small change in the placebo as well as the low-dose group, our primary analyses are two subgroup comparisons: high-dose vs. low-dose and high-dose vs. placebo and the two expected between-group effect sizes (high-dose vs. low-dose and highdose vs. placebo) are large (close to the within-group effect sizes in the pilot data). With 27 participants in each group, a two-sided two sample t-test has 80% power of detecting an effect size of 0.87 (Cohen's d) at 0.025 level to maintain the overall type I error rate at 0.05 level for the two group comparisons. We will recruit 30 participants for each group to allow

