for 10% dropouts. The subject enrollment will be split equally between the two sites (15 participants/group per site). For this study, our primary analysis is to use mixed model to test the interaction between group and time, which is expected to be more powerful than the two-sample t-test because all repeated measurements will be considered in modeling, baseline patient characteristics can be controlled statistically, and participants with missing data can be included for analysis.

D. Subject Criteria

a. Inclusion criteria/Exclusion criteria:

- i. Inclusion Criteria
 - Ages 35–65 years
 - BMI between 25-43 kg•m²
 - >5% risk for a cardiovascular event in the next 10 years according to the 2013 American College of Cardiology/American Heart Association risk calculator and/or 2 out of 5 metabolic syndrome risk factors (Triglycerides ≥ 150 mg/dL; HDL ≤ 40 mg/dL; Glucose ≥ 100mg/dL; Waist Circumference ≥ 102cm for males, 88cm for females; Blood pressure: ≥ 130mmHg systolic and/or 85mmHg diastolic or being treated for hypertension) and/or LDL-Cholesterol >120 mg/dl.
 - Stable doses of medications for 90 days
 - Willing to stop all NSAIDs and aspirin for 7 days prior to muscle biopsy

[figure not shown]
ii. Exclusion Criteria

- Smoking
- Previous use of statins
- Use of other medications or supplements that affect lipid profiles or body weight in the last 6 months
 - o e.g., fibric acids, bile acid sequestrants, nicotinic acids, fish oil
- Diagnosis of chronic diseases including CVD, other metabolic diseases (e.g., thyroid), current diagnosis and active treatment of cancer, HIV, or acquired immunodeficiency syndrome.
- Diagnosis of type 1 or type 2 diabetes at the time of screening (fasting blood glucose >126mg/dL). If evidence of type 2 diabetes outcome measures is detected during the course of the study (fasting glucose > 126 mg/dl or HbA1c > 6.5%) we will notify the participant to contact their physician.
- History of abnormal bleeding problems
- Currently taking (within the last 10 days) anti-platelet medication (Plavix), Warfarin, and other anti-coagulants (eliquis, pradaxa, and xarelto) medications.
- >2 fold upper normal limit (UNL) for ALT or creatinine
- Women who are pregnant or breastfeeding
- Individuals with polymorphism (SLCO1B1) known to be associated with susceptibility for statin induced myopathies (tested at screening)
- Currently enrolled in another research study

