- A. Statistical and Data Analysis: This project is a two-factor study. One factor is treatment group (between participants) and a second factor is time of data collection (0, 1, 6, and 12 months) (within subject). The data analysis will be carried out for the primary outcome variable of mitochondrial respiration in addition to other outcome variables (VO₂peak and insulin sensitivity, etc.). For each measure, its baseline measure and age will be added as covariates to adjust for the individual difference at baseline. Two-way interaction between treatment and time will be added in the model for testing if the outcome changes differently between groups over time. Additional variables, such as demographics, BMI, physical activity, etc. may also be included as covariates. If the test of trend difference is significant, then the comparison at each time point will also be considered to identify when the difference between groups reaches the maximum. Least Square Means will be used for the aforementioned comparisons. The statistical analysis will be performed with mixed procedure in STATA 13.1 (StataCorp LP, College Station, TX). Mixed model does not require complete data for a longitudinal study. Residual analyses will be conducted and efforts to address those will be made, including appropriate transformations.

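### Section V.A, read literally, uses each measure's baseline both as the month-0 outcome and as a covariate, and Sections II.C and V.A do not agree on one primary test

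*Combined protocol and SAP*

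**What the plan says.** Section V.A (Statistical and Data Analysis) describes a two-factor study: treatment group between participants, and "time of data collection (0, 1, 6, and 12 months) (within subject" as the second factor. It then states: "For each measure, its baseline measure and age will be added as covariates to adjust for the individual difference at baseline". For the test it says: "Two-way interaction between treatment and time will be added in the model for testing if the outcome changes differently between groups over time". For follow-up it says: "If the test of trend difference is significant, then the comparison at each time point will also be considered", with the aim of finding when the groups differ most, and "Least Square Means will be used for the aforementioned comparisons". The Stata mixed procedure is named. No random effects, residual covariance, estimation method or significance level is given.

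Section II.C (Sample size, statistical methods, and power calculation) sizes the trial on month 12. It says "our primary analyses are two subgroup comparisons: high-dose vs. low-dose and high-dose vs. placebo" and tests each "at 0.025 level to maintain the overall type I error rate at 0.05 level for the two group comparisons". Later in the same section it says "our primary analysis is to use mixed model to test the interaction between group and time".

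In Section II.E, the IVGTT and cardiovascular function are repeated only at months 6 and 12, so neither has a month-1 value.

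**The concern.** There are two separate problems.

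First, if month 0 is an outcome row and the same value is a covariate, the model is partly predicting a variable from itself. The fitted between-person variance is then too small. The least-squares mean differences that Section V.A prescribes inherit that variance, so their confidence intervals are too narrow.

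Second, the plan uses the word primary for two different hypotheses. Two pairwise month-12 differences at 0.025 each are not the same as one group-by-time interaction. Section V.A neither carries over the 0.025 split nor says whether its trend test is an omnibus interaction or a linear trend. What counts as a positive trial, and which p-value is reported first, is left open.

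**Working it through.** **1. The plan's own sample size.** Inputs from Section II.C: d = 0.87, two-sided alpha 0.025, 27 per group. The noncentrality is 0.87 × √(27/2) = 3.20 on 52 df, and exact t power is 0.81 (26 per group gives 0.793). Dropout: 27/0.9 = 30. The figure reproduces, but for one pairwise comparison at one visit. The omnibus interaction has (3−1) × (4−1) = 6 df. With 27 per group and an assumed high-dose decline of 0.2, 0.5 and 0.87 SD at months 1, 6 and 12, its simulated power is 0.69, 0.84 and 0.98 for correlation 0.3, 0.5 and 0.7. It therefore depends on a correlation that the plan does not give.

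**2. Interaction test.** A person's baseline is constant over that person's visits, so it cancels from every within-person contrast. In one simulated data set with 27 per group, all six interaction estimates agreed to four decimals with and without the covariate, and the standard error of the high-dose month-12 term was 0.2528 both ways. The test is therefore an unadjusted change-from-baseline test. Its month-12 variance relative to a baseline-adjusted contrast is 2(1−r)/(1−r²) = 2/(1+r), which is 1.54, 1.33 and 1.18 for r = 0.3, 0.5 and 0.7. The standard error is 24%, 15% and 8% larger.

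**3. Month-12 least-squares means.** Assumptions not in the plan: random-intercept fit, T visits, unit variance, equal correlation r, complete data, age omitted.
- The covariate varies only between persons, so its slope is that of the person mean on baseline: b = [1+(T−1)r]/T.
- The residual variance of a person mean is b − b². The within-person variance is 1−r, and it adds (1−r)(T−1)/T = 1−b. The model variance of one visit is therefore (b−b²) + (1−b) = 1−b².
- The true variance of the month-12 value minus b times baseline is 1 + b² − 2br.
- Model SE over true SE = √[(1−b²)/(1+b²−2br)].

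| Visits | r | b | Model variance | True variance | SE ratio |
|---|---|---|---|---|---|
| 4 | 0.3 | 0.475 | 0.774 | 0.941 | 0.907 |
| 4 | 0.5 | 0.625 | 0.609 | 0.766 | 0.892 |
| 4 | 0.7 | 0.775 | 0.399 | 0.516 | 0.880 |
| 3 | 0.3 | 0.533 | 0.716 | 0.964 | 0.861 |
| 3 | 0.5 | 0.667 | 0.556 | 0.778 | 0.845 |
| 3 | 0.7 | 0.800 | 0.360 | 0.520 | 0.832 |

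The standard error is thus 9–12% too small with four visits and 14–17% too small with three. Simulation at 15 to 27 per group with four visits gives 9–12% by REML and 11–16% by ML. In large samples a nominal 2.5% test on four visits rejects 4.2%, 4.6% and 4.9% of the time.

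**4. Overall error of the two pairwise contrasts (simulation, four visits, equal correlation).**
- Read off these means with no gate, at least one contrast at 0.025 is falsely significant in 6.8–8.2% of trials by REML and 8.6–10.8% by ML. Month-12 ANCOVA gives 4.5–4.7%.
- With an omnibus interaction gate at 0.05, the global-null figure is 1.7–2.0% by REML and 1.8–2.2% by ML.
- If both doses work equally, high versus low is the only true null. Gated, it is falsely significant in 2.6–4.5% by REML and 3.5–5.6% by ML.

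**The case against.** The list of months may only describe the design, with months 1, 6 and 12 intended as the responses. That stands as a possible reading, so double use is the literal reading and not the only one. It does not remove the need to say which is meant. On the other reading, the interaction asks only whether group differences change after month 1. With 27 per group and an effect of 0.87 SD constant from month 1, its simulated power is 4–6%.

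The interaction test is undistorted under equal correlation, and Section V.A gives the time-point comparisons a follow-up role. That stands too, and limits the reach of the standard-error problem.

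A reader might infer that overall type I error is inflated. The documents do not support this for the procedure in Section V.A, because time-point comparisons follow only after a significant first test. With an omnibus gate, the global-null error is well below 0.05. The least favourable case checked exceeds 0.05 only marginally, and only by ML. The larger ungated figures describe a procedure that Section V.A does not set out. A reader might also infer that either the interaction or a pairwise test may count as success. No section says so.

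If correlation decays with the time gap, a random-intercept fit distorts standard errors further. Most of that comes from the assumed covariance, and it occurs with baseline used once as well. It is a reason to state the structure, not a measure of the double use.

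Finally, the two comparisons in Section II.C could be meant as contrasts within the mixed model. That is plausible, but no section says so.

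**Conclusion.** The concern holds in a limited form. Read literally, Section V.A uses baseline twice. The treatment-by-time test is not harmed, but gets no baseline adjustment. The month-12 least-squares mean intervals are too narrow, with standard errors about 9–12% too small with four visits and 14–17% too small for insulin sensitivity. These sizes rest on a random-intercept fit and equal correlation of 0.3 to 0.7, neither of which the plan states. They reach primary inference only if Section II.C's two contrasts are read off those means.

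The conflict over the primary test needs no such assumption. Section II.C names both the pairwise comparisons and the interaction, Section V.A follows the interaction without an alpha, and the sample size supports the pairwise comparisons. This should be fixed before analysis.

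**What to change.** Use baseline once, by one of two routes:
- Model post-baseline visits only, with baseline, baseline-by-time and age as covariates. The visits are months 1, 6 and 12, or months 6 and 12 for measures with no month-1 visit, such as the IVGTT and cardiovascular function.
- Keep month 0 as an outcome and drop the baseline covariate. Optionally constrain baseline means to be equal across the randomised arms, which avoids most of the 24%, 15% and 8% loss of precision shown above.

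State the covariance structure, for example unstructured, and the estimation method. Naming the structure alone is not enough. If the double use stays and variances may differ by visit, a baseline slope of 1 makes every month-0 residual zero and the likelihood has no finite maximum.

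Reconcile Sections II.C and V.A by naming one primary test and its alpha. The two month-12 contrasts at 0.025 each match the stated sample size, with the interaction supportive. If month 0 is removed as an outcome, the interaction should not stay primary. If a gate is kept, say whether it is omnibus or linear trend.

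The cost is wording only, with no new data. The downside is that a trend test can be somewhat more powerful for a steadily progressive effect. With 15 per group and equal steps to 0.87 SD in the high-dose arm, simulated power is 58%, 73% and 92% for a linear trend, against 56%, 65% and 83% for the direct month-12 contrast, at correlation 0.3, 0.5 and 0.7.
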